571 standard and the Data Protection Regulation and the Data Protection act. Surplus material from
572 the biopsies will be kept in a research biobank for up to five years after study termination in case
573 it will be necessary to do any further analyses. After this period the samples will be destroyed.
574 All extra analyses will only be performed after approval from The National Committee on Health
575 Research Ethics. Biological material will not be sent to any other countries.

576 **6.7 Procedures for breaking randomisation code**

577 Sponsor will receive a set of coded envelopes with all randomization numbers and another set
578 of coded envelopes will be delivered separately together with the study drug/placebo. In case that
579 the treatment allocation needs to be revealed, the envelopes can be opened. The envelopes are
580 stored and available at the department 24/7. The investigator can be reached by [contact].

582 **7. Quality Assurance and Audit**

583 **7.1. Insurance and Indemnity**

584 Insurance and indemnity for trial participants and trial staff is covered within the hospital's
585 liability insurance

586 **7.2. Trial Conduct and Monitoring**

587 This trial will be conducted in adherence with the protocol, International Conference on
588 Harmonisation Good Clinical Practice E6 (ICH-GCP) and the applicable regulatory
589 requirements. All study documents and standard operating procedures will be prepared to
590 ensure compliance with GCP.

591 The investigators will ensure that all study procedures are followed and any deviations
592 documented and investigated.

593 The study will be performed in accordance with GCP. The GCP-unit, Copenhagen
594 (Frederiksberg hospital, [name]) will
595 monitor the study. The Danish Data Protection Agency will be notified about this study.

596 **7.3. Record Retention and Archiving**

597 In compliance with the ICH-GCP guidelines, the Principal Investigator will maintain all records
598 and documents regarding the conduct of the study. These will be retained for at least 7 years or
599 for longer if required. If the responsible investigator is no longer able to maintain the study
600 records, a second person will be nominated to take over this responsibility.

601 **7.4. Risk Assessment**

602 There is little additional risk or benefit to the individual participant by entering this study. The
603 study drug is a standard treatment option for certain rheumatoid diseases and the risks
604 associated with the treatment are well documented with the most common being infection.
605 During the study we will be giving the study drug at the daily recommended dose. Risks related
606 to the clinical procedures in the study can be minor pain, bruise and infection when taking blood
607 samples. Minor pain and bruising during blood pressure measuring. Redness and irritation of
608 skin related to patch testing. Redness, irritation, minor risk of bleeding, infection and minor
609 scarring related to the biopsies. Minor radiation risk exposes the participant to about 0.1 mSv
610 (corresponding to 1-2 weeks of background radiation during chest x-ray. Background radiation
611 is 3 mSv/year). Participants in the study will receive either an active drug or placebo. The results
612 of this study will help inform clinical treatment decisions that will benefit society.

613 **7.5. Confidentiality**

614 Individual participant medical information obtained as a result of this study is considered
615 confidential. Participant confidentiality will be further ensured by utilising identification code
616 numbers to correspond to treatment data in the computer files.

617 Data generated as a result of this trial will be available for inspection on request by the
618 participating physicians, the ethics committees, host institutions and the regulatory authorities.

619 **7.6. Ethical Considerations**

620 Participants will be provided with written and oral information on this study and will only be
621 enrolled when given their written informed consent. The study will be designed in accordance to
622 the Helsinki-declaration. Herlev and Gentofte Hospital will ensure that collection and processing
623 of personal data comply with national legislation on data protection and privacy. Participants will

624 not directly benefit from the study. All procedures (biopsy, blood tests and allergies) are
625 performed routinely in the department, anakinra is already used for individual patients with
626 autoinflammatory diseases. However, it will extend our knowledge about mechanisms involved
627 in ACD, which may lead to new treatments of the disease. Severe ACD is associated with
628 known reduced life quality, disruption of sleeping and affected work life. Thus, studies
629 investigating ACD are needed.

630 **8. PUBLICATION AND DISSEMINATION POLICY**

631 The results of the study will be submitted for publication in a peer review journal as soon as
632 possible after analysis. All investigators will be named in the acknowledgments, detailing their
633 role in the study. Participants will not be identified in any publications.

634 **9. STUDY FINANCES**

635 **9.1. Funding source**

636 This study is fully funded by the LEO Foundation and Aage Bang Foundation (DKK 1.070.000).
637 The University of Copenhagen administrates the economy. None of the investigators have any
638 commercial interests in the study. The LEO Foundation has no influence on this study. The
639 research conducted is fully independent of the LEO Foundation.

640 **9.2. Participant stipends and payments**

641 Participants will be economically compensated to participate in the trial since they will not
642 directly benefit from the study. Travel expenses will be covered for any costs incurred for
643 hospital visits. Participants will be compensated with 10.000 DKK for disadvantage, medical
644 treatment, visits, and skin biopsies upon completion of the study. The economical compensation
645 is taxable income. Participants will receive 500 DKK as compensation for their time if they're
646 found non-eligible after the screening visit and participants who drop out prior to completion will
647 be economically compensated according to the number of visits and biopsies they have
648 participated in.

649 **10. REFERENCES**

650 1. Thyssen JP, Linneberg A, Menné T, Johansen JD. The epidemiology of contact allergy in
651 the general population – prevalence and main findings. *Contact Dermatitis* [Internet].
652 2007 Nov;57(5):287–99. Available from: <http://doi.wiley.com/10.1111/j.1600-0536.2007.01220.x>

654 2. Henrik Nielsen, Allan Linneberg, To N. Allergic Contact Sensitization in an Adult Danish
655 Population: Two Cross-sectional Surveys Eight Years Apart (The Copenhagen Allergy
656 Study). *Acta Derm Venereol* [Internet]. 2001 Jan 1;81(1):31–4. Available from:
657 <https://medicaljournals.se/acta/content/abstract/10.1080/00015550116939>

658 3. Simonsen AB, Deleuran M, Johansen JD, Sommerlund M. Contact allergy and allergic
659 contact dermatitis in children - A review of current data. *Contact Dermatitis*. 2011.

660 4. Kadyk DL, McCarter K, Achen F, Belsito DV. Quality of life in patients with allergic contact
661 dermatitis. *J Am Acad Dermatol* [Internet]. 2003 Dec;49(6):1037–48. Available from:

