73 • Kineret®, Swedish Orphan Biovitrum, 100 mg/0.67 mL, injectable fluid for s.c.
74 administration.

75 The pharmaceutical company will be notified about the trial. More details regarding the chemical
76 and pharmacological properties of the study drug can be found in the Summary of Product
77 Characteristics.

78 The control group will receive placebo in the form of sterile isotonic saline water injections.

79 • Sodium chloride Fresenius Kabi 9 mg/ml

80 **1.2.2 Packaging and Labelling**

81 The study drug and placebo will be specially packaged and labeled by Region Hovedstaden's
82 pharmacy and they will be the responsible unit for distribution of the study drug and placebo.
83 The administering personnel are unblinded to treatment but participants and investigators are
84 blinded to the treatment allocation.

85 **1.2.3 Storage and administration**

86 The study drug will be stored as per the manufacturer's instructions at The Department of
87 Dermatology and Allergy, Herlev Gentofte Hospital. The clinical trials personnel at the hospital
88 will administer the medication and keep detailed administration records. Double checking of
89 medication will be performed.

90 **1.2.4 Known Side Effects**

91 Known side effects to anakinra are listed below:

92 >10%: Headache, local reaction at the site of injection

93 1-10%: Serious infections, neutropenia

94 0.1-1%: Allergic reactions (including angioedema and anaphylaxis)

95

96 **2. STUDY PURPOSE AND OBJECTIVES**

97 **2.1. Purpose**

98 The purpose of this study is to characterize the clinical effect of inhibiting IL-1 β in ACD, and to
99 investigate the role of IL-1 β in the maintenance and function of epidermal T_{RM} cells. We expect
100 that this knowledge can lead to the development of more specific treatments and potential cures
101 for patients with ACD.

102 **2.2. Hypothesis**

103 IL-1 β is a key cytokine in immune responses to contact allergens. Epidermal-resident memory
104 CD8+ T (T_{RM}) cells lead to an increased production of IL-1 β in skin cells upon challenge of the
105 skin with contact allergens. However, the effect of IL-1 β on epidermal T_{RM} cells is not known.
106 We hypothesis that a positive feedback loop exists where IL-1 β from skin cells boost the
107 epidermal T_{RM} cells to ensure their maintenance and increase their pathological effector function
108 in form of production of IFN- γ and IL-17A production that again stimulate the skin cells to
109 produce IL-1 β .

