140 dermatitis. Patient reported outcomes will include Patient's Global Assessment Score (PtGA).
141 Treatment effect will be defined as a difference in score between the two groups on the scoring
142 systems used.

143 **3.2.2. Secondary Outcome Measure**

144 From each group, blood and biopsies from seven individuals will be used for single cell RNA
145 sequencing (sc-RNAseq), and/or digital spatial profiling. Skin biopsies from the remaining three
146 individuals will be used for immunohistochemistry, flowcytometry (staining with anti-CD3, anti-
147 CD8, Ki67, anti-IL-1 β) and/or qPCR (IFN- γ , IL-17A and IL-1B). Treatment effect will be defined
148 as a reduction in number of T-cells, cytokines and proliferative markers in the treatment group
149 compared to placebo.

150 **3.3. Stopping Rules and Discontinuation**

151 The Department of Dermatology and Allergy, Herlev and Gentofte Hospital can discontinue the
152 trial at any time for failure to meet expected enrolment goals, for safety or any other
153 administrative reasons. Participants and The Regional Committee on Health Research Ethics
154 will be informed in given case. The following may result in the trial being terminated

155 • Major safety concerns.
156 • Insurmountable issues with trial conduct (e.g. poor recruitment, loss of resources).

157 **3.4. Randomization and Blinding**

158 **3.4.1. Randomization**

159 The randomization will be based on a computer-generated code using random permuted blocks
160 of varying size or by sealed envelope. Access to the sequence will be confined to Region
161 Hovedstadens Pharmacy. Participants will be allocated in a 1:1 ratio to the anakinra and
162 placebo treatment arms. The sequence of treatment allocations will be concealed until
163 interventions have all been assigned and recruitment, data collection, and all other trial-related
164 assessments are complete.

165 **3.4.2. Blinding**

166 The investigators and assessors will be blinded to treatment allocation until the results of the
167 outcome measurements are recorded. Only the administering personnel will be unblinded to
168 treatment allocation and know the allocation sequence. Trial participants will also be blinded to
169 treatment allocation until the end of trial.

170 **3.5. Trial Management**

171 The trial and all clinical procedures will be conducted at The Department of Dermatology and
172 Allergy, Herlev and Gentofte Hospital. All laboratory analyses of tissue specimens will be

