271 done before informed consent has been obtained.

272 The investigator will inform the participant of any relevant information that becomes available
273 during the study, and will discuss with them, whether they wish to continue with the study. If
274 applicable they will be asked to sign revised consent forms.

275 If the Informed Consent Form is amended during the study, the investigator shall follow all
276 applicable regulatory requirements pertaining to approval of the amended Informed Consent
277 Form by the REC and use of the amended form (including for ongoing participants).

278 Informed consent declaration S3 from The National Committee on Health Research Ethics will
279 be used.

280

281 **3.8. Study Treatment and Regimen**

282 **3.8.1. Study Treatment**

283 At day 20 (week 3) participants will be randomized to receive either:

Anakinra 100 mg/0,67 ml

OR

284
NaCl solution 9 mg/ml

286

287 Investigator and participants will be blinded to treatment allocation. The study drug and placebo
288 will be administered by unblinded personnel. The study drug or placebo will be administered
289 subcutaneously for six consecutive days, starting on day 20.

290 At any point, if the participant experiences a life-threatening adverse reaction, treatment will be
291 terminated.

292

293 **3.8.2. Rescue Medication**

294 Use of any systemic or topical immunosuppressant/immune-modulating drugs is strongly
295 discouraged to prevent potential systemic effects not related to study intervention. Accidental
296 use of immunosuppressant or immune-modulating drugs during the study period will be
297 classified as a protocol deviation.

298 **3.8.3. Prohibited concomitant medication**

299 The administration of live virus vaccines and any form of immunosuppressive drug is not
300 permitted for all participants. Participants should continue to take medications for other
301 conditions as normal. However, if it is anticipated that the participant will need a live virus
302 vaccine during the intervention phase, they will be ineligible for entry into the study.

303 **3.8.4. Caution with other concomitant medications**

304 Concomitant use of other biological pharmaceuticals is not recommended due to an increased
305 risk of infection.

306 **3.8.5. Adherence**

307 To ensure adherence, designated personnel will administer the study drug. If a participant does
308 not adhere to the administration schedule, it will be classified as a protocol deviation.

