- 510 • If the event is deemed a SUSAR, shall, within seven days, complete the CIOMS form
511 and send to the DMA.
- 512 • Shall inform the REC using the relevant reporting form found on the REC's web page
513 within seven days of knowledge of the event.
- 514 • Shall, within a further eight days send any follow-up information and reports to the DMA
515 and REC.
- 516 • Make any amendments as required to the study protocol and inform the ethics and
517 regulatory authorities as required.

518 **5.5. Collection of Adverse Event Data**

519 This study investigates a widely used drug, anakinra, for which the side-effect profile is well
520 established. For this reason, only adverse events that are known side-effects will be collected
521 (detailed in section 4.2.4, Known side effects) i.e. only adverse reactions will be collected.

522 At each mandatory study visit, the investigator will record whether the participant had
523 experienced any of the reportable adverse events. The investigator can also record any other
524 significant adverse events that are not listed if deemed clinically relevant.

525 All available sources of information will be used to collect information on adverse events
526 including hospital notes, the participant diary and discussion with the participant. Any adverse
527 events reported will be graded according to a modified version of the Common Terminology
528 Criteria for Adverse Events v3.0.

529 **6. Ethics Committee and Regulatory Aspects**

530 **6.1. Ethical and Regulatory Approval**

531 The trial will not be initiated before the protocol, informed consent forms and participant and
532 information sheets have received approval / favourable opinion from the DMA and REC.

533 The trial will be conducted in accordance with the ethical principles that have their origin in the
534 Declaration of Helsinki, 1996; the principles of Good Clinical Practice, in accordance with the
535 Medicines for Human Use Regulations, Statutory Instrument 2004, 1031 and its subsequent
536 amendments.

537 **6.3. Case Report Forms**

538 Each participant will be assigned a trial identity code number, allocated at randomisation, for
539 use on the case report forms (CRFs), other trial documents and the study database. The
540 documents and database will also use their initials (of first and last names separated by a
541 hyphen or a middle name initial when available) and date of birth (dd/mm/yy).

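### The blinded investigator records injection-site reactions at visits where the patches are scored, and nothing keeps the scorer from this information, so the IGA/ICDRG scores can be unblinded

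*Combined protocol and SAP*

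**What the plan says.** - **Known effects (1.2.4).** The most frequent band for anakinra reads ">10%: Headache, local reaction at the site of injection". No upper figure is given.
- **Comparator (1.2.1).** "The control group will receive placebo in the form of sterile isotonic saline water injections". Nothing is said about local reactions to saline.
- **Blinding (3.4.2).** "The investigators and assessors will be blinded to treatment allocation until the results of the" outcome measurements are on record. "Only the administering personnel will be unblinded to" the allocation.
- **Adverse-event collection (5.5).** Routine collection is limited to the listed known effects ("detailed in section 4.2.4, Known side effects) i.e. only adverse reactions will be collected"). The list is in fact in 1.2.4; the wrong cross-reference does not change the meaning. "At each mandatory study visit, the investigator will record whether the participant had" any of these events, and the sources include the diary and talking with the participant.
- **Primary outcome (3.2.1).** The patch sites are graded on site and blinded, by IGA and ICDRG. The participant also gives a global score (PtGA). The section does not name the scorer or say which visit's score is primary.
- **Sample size (4.2).** 10 per arm, to detect a one-point reduction in clinical score.

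**The concern.** A blinded role is told to ask about an effect that the protocol itself attributes to the active drug, at visits where the outcome is graded by eye. Headache, which shares the top frequency band, says little about allocation. A local reaction at the injection site can be seen and says more. If the person grading the patch learns of it, that person may guess the arm.

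IGA and ICDRG are judgement scales and the target difference is one point, so knowledge of allocation could move a grade. The likely direction is towards lower grades on anakinra, the direction in which the trial hopes to find an effect. With 10 participants per arm, a few altered grades count.

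**Working it through.** **1. Where recording and scoring meet.** The schedule table in 3.9.1 is set against the visit lists for days 21 to 25.

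| Day | Adverse events recorded | Patch reaction evaluated | Comment |
|---|---|---|---|
| 21 | table and text | table and text | reading is listed before the second patch is applied |
| 22 | table and text | table only | second patch is not removed until day 23 |
| 23 | table and text | table and text | second-challenge reading |
| 24 | table and text | table and text | second-challenge reading |
| 25 | table and text | table only | visit list has no evaluation |

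For the second challenge, table and text agree on both tasks only on days 23 and 24. By the day 23 visit a participant has had injections on days 20, 21 and 22. On both days the visit list puts adverse-event recording above patch evaluation, although the protocol does not say that the lists give the working order.

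**2. Safeguards looked for.** No section gives the recording to the unblinded staff, separates recorder from scorer, fixes the order of the two tasks, has injection sites covered, or assigns the scoring to someone without access to adverse-event data.

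**3. The plan's own figure.** Section 4.2 gives no SD, test or sidedness, so 10 per arm cannot be reproduced. Only the implied SD can be found. With a two-sided 5% level and the normal approximation:

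SD = 1 / [√(2/10) × (1.960 + 0.842)] = 1 / (0.447 × 2.802) = 0.80

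The two-sample t-test gives 0.75, which is used below.

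**4. How often the cue could appear.** With reaction rate q in the anakinra arm, P(at least one of 10 reacts) = 1 − (1 − q)^10. Only the lower bound of 10% comes from the documents. The 30% and 50% rates are assumptions.

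**5. What it could do to the result.** Let qA and qP be the reaction rates on anakinra and saline, u the share of reactions that the scorer learns of and reads as anakinra, and b the grade reduction that follows. Then

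shift in mean difference = (qA − qP) × u × b.

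None of qP, u or b is in the documents. The table sets qP = 0 and u = 1, both unfavourable choices, and b = 0.5 or 1. The false-positive rate is for a two-sided 5% t-test with no drug effect, 10 per arm and SD held at 0.75. The noncentrality is shift / (0.75 × √(2/10)); for a shift of 0.3 this is 0.3 / 0.335 = 0.89.

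| qA | P(at least 1 of 10) | Shift, b = 0.5 | False positive | Shift, b = 1 | False positive |
|---|---|---|---|---|---|
| 10% | 65% | 0.05 | 5.2% | 0.1 | 5.9% |
| 30% | 97% | 0.15 | 7.1% | 0.3 | 13.5% |
| 50% | 99.9% | 0.25 | 10.9% | 0.5 | 29.2% |

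A saline rate above zero shrinks these figures. With qA = 30%, qP = 10% and b = 0.5 the shift is (0.3 − 0.1) × 0.5 = 0.10. If the two rates are equal, the shift is zero.

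**The case against.** **The scorer may not be the recorder.** A reader might infer that one person must do both tasks. The documents do not say so. Section 3.4.2 names investigators and assessors, 3.2.1 does not name the scorer, and the schedule assigns neither task to a person. This stands. What remains is that no text keeps the scorer, whoever it is, away from the information.

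**The scores need not be unblinded.** Saline injections may also leave a mark, the frequency in 1.2.4 is not tied to a six-day course, and the injection site on the body is not stated. The documents support that scores can be unblinded, not that they will be.

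**The table of shifts is not an estimate.** A reader might take 0.1 to 0.5 points as the expected bias. Those figures assume that every reaction is noticed and correctly read, that it costs a full grade, and that saline causes none. The documents support none of this. At the listed lower bound the effect on false positives is slight.

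**The overlap is narrower than days 21 to 25.** The table suggests all five days, but the visit lists do not bear this out for days 22 and 25, and the day 21 reading is not of the second challenge. Readings on days 42 to 45 come at least 17 days after the last injection (42 − 25), with no adverse-event recording marked in the table. A scorer unmasked earlier could still remember, but since no primary visit is named, exposure of the decisive score is not established.

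**Safety duties limit the remedy.** It may seem natural to hide every listed effect from the scorer until scoring ends. The list in 1.2.4 includes serious infections and anaphylaxis, and 5.1 to 5.4 require the Chief Investigator to assess causality and to be told at once of reportable serious reactions. The remedy therefore has to be confined to non-serious local reactions.

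**Conclusion.** The point holds as a gap in the protection of blinding. The blinded investigator is directed to record a visible, drug-attributed effect at the visits where the patches are graded, on days 23 and 24 by table and text alike, and nothing shields the scorer. The IGA and ICDRG scores can be unblinded and could be biased in favour of anakinra.

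The size cannot be determined from the documents. It depends on the difference in reaction rates between the arms, on how often the scorer learns of a reaction, and on how much a grade then moves. It could be negligible. The point rests on the assumption that anakinra causes more local reactions than saline, which the documents suggest but do not quantify. The change is worth making because it costs little, not because bias has been shown.

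**What to change.** In 5.5 and in the dosing-visit lists (days 20 to 25):

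- The unblinded administering personnel record non-serious injection-site reactions on a separate page that is not shown to the person who scores the patches.
- The scorer examines only the lower back, with injection sites covered, and records the score before any adverse-event discussion at that visit.
- All other adverse events, and all serious or clinically significant events of any kind, go to the investigator and Chief Investigator without delay, as 5.1 to 5.4 already provide. The page stays open to the Chief Investigator for causality assessment, so the scorer should be someone else.
- Name the scoring role in 3.2.1 or 3.4.2, and reconcile the table with the visit lists on patch evaluation on days 22 and 25.

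The cost is one reassigned CRF page and a visit-order instruction. The administering personnel already see every participant on each dosing day, and the sample size stays at 20. If the Chief Investigator was to score, another scorer is needed. The downside is that minor local reactions are recorded by staff who know the allocation, so their reported frequency may be coloured by that knowledge.

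The change does not protect PtGA, which is scored by the person who feels the reaction. The protocol should state this as a limitation.
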